#### 5.6 AUDICOR® AM device setup and second use

Following the overnight wear, removal and reapplication testing, and final removal of the WCD device, subjects will wear the AUDICOR device again for 15 minutes while sitting quietly (for details see section 5.4).

### 6. DATA COLLECTION

ECG and heart sounds data recorded by the AUDICOR® AM devices during the testing will be transferred from the data storage cards to the sponsor provided computer. Study coordinators will perform a manual download to transfer each subject's baseline and all automatically recorded ECG data by the WCD to the ZOLL servers. The WCD device will also collect and store complete recordings of ECG data, heart sounds data, device performance data, and subject-device interaction data. These data will be stored in the WCD monitor's removable storage and will be extracted upon return of the device to ZOLL. Case report forms will be used to collect general demographic and medical history information from subjects enrolled in the study. In addition, the study coordinator will record the start and end times of each activity of daily living maneuver and the removal and reapplication times of the WCD device.

### 7. DATA ANALYSIS

Data from all subjects in the study will be considered and/or analyzed. At a minimum, the full sample set as well as the subsample set (measurements made every five minutes and sleep scores) of the following variables will be analyzed:

- Electromechanical activation time (EMAT): Time from onset of QRS in the ECG signal to the first heart sound, S1.
- Percentage EMAT (EMATc): EMAT normalized by heart rate.
- Left ventricle systolic time (LVST): Time interval from S1 to the second heart sound, S2.
- Percentage LVST (%LVST): LVST normalized by heart rate.
- Presence of the third and fourth heart sounds, S3 and S4, respectively.
- Systolic dysfunction index (SDI): A multiplicative combination of ECG and heart sound parameters derived from QRS duration, QR interval, EMAT, and S3 strength.
- Sleep disordered breathing index (SDBI): A score to detect sleep disordered breathing events.

Equivalence of the modified WCD device to the AUDICOR device will be established by comparing the full sample EMAT data during quiet sitting (see section 8 for details). Additional descriptive statistics and qualitative analysis will be used to compare the heart sounds measures for each subject and as a group between the AUDICOR device and WCD device; across various activities of daily living maneuvers; before the removal and after the reapplication of the WCD; and across time for all the devices. These analysis are for observational purposes only and there are no endpoints associated with them.

## 8. EVALUATION OF RESULTS

Equivalence of the modified WCD device to the AUDICOR device will be established by comparing the full sample EMAT data during quiet sitting. EMAT was chosen to establish equivalence because previous studies have shown the utility of EMAT in predicting or identifying patients with left ventricular dysfunction . The two one-sided test (TOST)  will be used to test equivalence. Because measurements from the two devices (WCD and AUDICOR) are made on the same subject, a paired T-test will be used. The equivalence margin will be set at 12-ms, which is 10% of the 120-ms EMAT threshold previously used to identify patients with left ventricular dysfunction (K051450 and K070136). Using TOST, equivalence will be established at  $\alpha = 0.05$  significance level if a  $(1 - 2\alpha) * 100\%$  confidence interval for the average difference in EMAT (WCD-AUDICOR) is contained within the interval [-12, 12].

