### Intervention

First, participants will wear the AUDICOR® AM device for 15 minutes while sitting quietly. Then, the AUDICOR device will be removed and the participants will wear the WCD for 15 minutes while sitting quietly. Next, while wearing the WCD, participants will perform various activities of daily living, including at least 6 hours of overnight wear. Finally, the WCD will be removed and the participants will wear the AUDICOR® AM again for 15 minutes while sitting quietly.

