## 3. OBJECTIVES

The objectives of the study are to:

- 3.1 Compare the heart sound measurements recorded by the AUDICOR® AM device versus those recorded by the WCD while subjects are sitting quietly.
- 3.2 Observe the variation of heart sound measurements recorded by the WCD across subjects with specific physical maneuvers, time, and repositioning (due to removal and reapplication) of the WCD.
- 3.3 Observe measurements of the sleep-disordered breathing index recorded by the WCD.

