## 5.5 WCD device setup and use

**Figure 4:** WCD vest placement on the subject with location of the WCD heart sounds sensor.

Application of the WCD will follow the procedures described in the LifeVest® Clinician Manual and will include:

- Programming the monitor and entering subject's identification number.
- Measuring the subject's chest size with the measuring tape centered at the xiphoid.
- Selecting the appropriate vest/garment size based on the chest size measurement.
- Assembling the garment with the monitoring and defibrillation electrodes, with the electrode belt disconnected from the monitor.

- Placing the assembled garment on the subject such that all clothing, including underwear, is worn over the device and not under it.
- Marking the location of the WCD heart sounds sensor in the case report form.
- Inserting a fully charged battery, connecting the electrode belt to the monitor, and starting the baseline process.
- Ensuring that the baseline process is successfully completed.
- Setting up the charger to allow for downloading of WCD monitoring data.

Following 5 minutes of inactivity for ECG stabilization, subjects will sit quietly for 15 minutes. The beginning of sitting will be marked by tapping the WCD front therapy electrode twice and noting the time. During testing, subjects are expected to sit in a chair comfortably, with their back straight. Instruct them to be relaxed, quiet and still as possible while sitting. At the end of 15 minutes, the front therapy electrode will be tapped twice and the time noted.

Subjects will then perform the activities of daily living (ADL) maneuvers listed below for 10 minutes each.

- 5.5.1 Standing
- 5.5.2 Lying on the back
- 5.5.3 Lying on the left side
- 5.5.4 Lying on the right side
- 5.5.5 Sitting and leaning forward

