After settling into the new position, the front therapy electrode will be tapped twice by the test administrator, the time after tapping will be noted as the start time, a manual recording will be performed by holding the response buttons for 3-seconds, and at the end of 10 minutes the front therapy electrode will be tapped and the time will be noted as the stop time. After all ADL maneuvers are complete, the study coordinator will remove the WCD device by disconnecting the electrode belt, unplugging the battery from the monitor, and removing the garment off the subject. After five minutes, the garment will be reapplied and then electrode belt and battery will be reconnected to the monitor. The subject will wear the device for 10 minutes while sitting quietly. The removal and reapplication times will be noted.

Following the removal and reapplication section, the subject will continue to wear the WCD until the total use of the device is 12 to 16 hours, with at least 6 hours of overnight wear. During the overnight wear the subject will be expected to sleep at the testing site. In addition, subjects will fill a diary (see Appendix A) to note their non-testing WCD activities before and after sleeping; any non-testing activity that causes the device to alarm; and any activity while sleeping that causes the WCD to alarm.

After the overnight wear, removal and reapplication of the WCD device will be repeated, following the procedure as described previously, and the subject will wear the device for 10 minutes while sitting quietly. At the end of the testing, recording from the WCD device will be terminated by removing the battery and the garment will be removed from the subject. Data from the WCD device will be downloaded to the ZOLL servers. In addition, at the end

---

of testing each subject, the WCD monitor will be cleaned, packed appropriately, and returned to ZOLL.

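### Must Section 8 be rewritten because it does not say which of the five quiet-sitting sessions enter the EMAT equivalence test?

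*Combined protocol and SAP*

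**What the plan says.** Sections 5.4 to 5.6 schedule five quiet sittings, always in this order:

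- A1: AUDICOR, 15 minutes.
- W1: WCD, 15 minutes, after a settling period ("Following 5 minutes of inactivity for ECG stabilization, subjects will sit quietly for 15 minutes").
- W2: WCD, 10 minutes, after the first removal and reapplication.
- W3: WCD, 10 minutes, the next morning ("After the overnight wear, removal and reapplication of the WCD device will be repeated, following the procedure as described previously").
- A2: AUDICOR, 15 minutes, last.

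Section 8 defines the confirmatory data in one sentence: "Equivalence of the modified WCD device to the AUDICOR device will be established by comparing the full sample EMAT data during quiet sitting". The test is a paired-t TOST with a 12 ms margin. Section 7 explains full sample only by contrast: "the full sample set as well as the subsample set (measurements made every five minutes and sleep scores". That describes sampling density and is not a rule about sessions.

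Three places bear on the intended sessions. Objective 3.1 is to "Compare the heart sound measurements recorded by the AUDICOR® AM device versus those recorded by the WCD while subjects are sitting quietly". Objective 3.2 separately covers variation "with specific physical maneuvers, time, and repositioning (due to removal and reapplication) of the WCD". The Intervention summary describes one quiet AUDICOR sitting, one quiet WCD sitting and then the closing one: "Finally, the WCD will be removed and the participants will wear the AUDICOR® AM again for 15 minutes while sitting quietly". It does not mention W2 or W3. Section 7 also lists comparisons around reapplication, and over time for both devices, among the additional descriptive work, and says of that work: "These analysis are for observational purposes only and there are no endpoints associated with them".

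**The concern.** A paired t-test needs one difference per subject, and the plan does not define it. Any non-empty set of the three WCD sittings could be paired with any non-empty set of the two AUDICOR sittings. That gives 7 × 3 = 21 definitions before any weighting is chosen.

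The definitions respond differently to a change in resting EMAT overnight, and the fixed order means that such a change can be counted as a device difference. The planning difference of -7.26 ms lies 4.74 ms from the margin, so a shift of about 1 ms matters. The choice could also be made after the data are seen. A natural remedy is to prescribe ½[(W1 − A1) + (W3 − A2)], which reverses the device order at the two ends and uses sittings already recorded.

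**Working it through.** **Inputs.** Margin 12 ms and α = 0.05 (Section 8). Absolute mean difference 7.26 ms, SD 8.36 ms, seven pilot subjects, n = 27 (Section 9.1). The documents give no overnight change (D), drift, order effect or reapplication shift (R). All values for these below are assumptions.

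**The plan's own figures.** The pilot interval is -7.26 ± 1.943 × 8.36/√7 = -7.26 ± 6.14 = (-13.40, -1.12). The printed limits are -13.4 and -1.13, so the planning difference is negative. For the sample size, [8.36 × (1.645 + 1.282)/(12 − 7.26)]² = 26.6, which rounds up to 27.

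**Headroom.** At n = 27 the 90% half-width is 1.706 × 8.36/√27 = 2.74 ms. The observed mean must lie within 12 − 2.74 = 9.26 ms of zero, which leaves 2.00 ms beyond 7.26. Exact TOST gives 5.0% false equivalence at -12 ms and 88.9% power at -7.26 ms.

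**Share of an overnight step D counted as device difference** (D is added to W3 and A2):

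| Definition | Share |
|---|---|
| W1 − A1 | 0 |
| W1 − mean(A1, A2) | -1/2 |
| All sittings, pooled by minutes | 10/35 − 15/30 = -0.21 |
| ½[(W1 − A1) + (W3 − A2)] | 1/2 − 1/2 = 0 |

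With an assumed |D| of 2 ms and SD held at 8.36, W1 against both AUDICOR sittings shifts by 1 ms. False equivalence and power are then 14.9% and 96.6% if the shift is towards zero, or 1.2% and 73.2% if away. Pooling by minutes shifts by 0.43 ms: 8.3% and 93%, or 2.8% and 83%.

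**W1 − A1 under drift.** Assume 5 ms over 720 minutes and 20 minutes of set-up. The gap between session centres is 7.5 + 20 + 5 + 7.5 = 40 minutes, so the shift is 5 × 40/720 = 0.28 ms. False equivalence is 7.0%, or power 85% with the other sign. An order effect enters W1 − A1 in full: an assumed 1 ms gives the same figures as the 1 ms shift above.

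**The two-end contrast.** With equal set-up times, the same drift leaves ½ × (20 − 12.5) = 3.75 minutes, or 0.03 ms, and a symmetric order effect cancels. A shift R in W3 enters at R/2, whereas W1 − A1 has none of it.

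The SD of this contrast depends on which sittings produced 8.36, and Section 9.1 does not say. With independent, equal session errors (variance 1 per session), the contrast has variance 1. The variance is 2 for W1 − A1, 1.5 for W1 against both AUDICOR sittings, and (15² + 10² + 10²)/35² + 1/2 = 0.847 for pooling. The contrast SD is then 8.36/√2 = 5.91, 8.36/√1.5 = 6.83 or 8.36/√0.847 = 9.08. For an assumed R of 2 ms (a 1 ms shift):

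| Contrast SD | Power, R = 0 | False equivalence, towards zero | Power, away from zero |
|---|---|---|---|
| 5.91 | 99% | 21.5% | 94% |
| 6.83 | 97% | 18.3% | 87% |
| 9.08 | 84% | 13.8% | 67% |

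The contrast gains only if R is smaller than D or the order effect, and the documents do not show that it is.

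**Choice after the data are seen.** Let f be the assumed share of single-pair variance that is session noise, from 0.10 to 0.75. By simulation at a true difference of -12 ms, taking whichever of four plausible definitions passes gives 6.4% to 9.2% false equivalence. Taking the best of all 21 gives 8.9% to 19.4%.

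**The case for a change.** The strongest case for a change is that no sentence excludes W2 or W3. Both are quiet sittings, so the words of Section 8 and objective 3.1 cover them. Section 7's descriptive list also includes comparisons between the devices, so it does not by itself fix the confirmatory set. Even without W2 and W3, the comparator could be A1, A2 or both, and using both with W1 alone counts half of any overnight change as device difference. This is the only confirmatory test, and the selection figures do not depend on D.

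Much of this stands. The session rule is missing, and an analyst must write it down before seeing EMAT results. The range is narrower than 21, however. The summary, the split between objectives 3.1 and 3.2 and the observational status of reapplication and time comparisons point to W1 against A1, perhaps with A2. A definition that keeps W3 but drops A2, for example, has no support in the text. The best-of-21 figures describe someone who tries every pairing and keeps one that passes, which nothing in the plan suggests.

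The order confounding in W1 − A1 also stands. It comes from the fixed-order design. The available remedy admits W3, which is shorter, follows a reapplication and has no stated settling period. Requiring both pairs would also drop subjects with a valid first pair, although Section 7 says that data from all subjects are to be considered.

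**Conclusion.** No change follows. The missing session rule is a gap that an analyst fills sensibly from the rest of the protocol, by fixing W1 against A1, or W1 against both AUDICOR sittings, before analysis. Under the first, an overnight step leaks nothing and the assumed drift leaks 0.28 ms. Under the second, half of any overnight change leaks, which the reader should keep in mind. The descriptive comparisons over time and around reapplication that Section 7 already plans would show A2 − A1 and W2 − W1, and so indicate whether such shifts are present.

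The two-end contrast is a reasonable sensitivity analysis but not a demonstrably better primary definition. It exchanges an assumed drift or order bias for an assumed reapplication shift: 2 ms in W3 costs up to 21.5% false equivalence, or power down to 67%. All these sizes rest on assumed D, R, drift and order effects and on independent, equal session errors. No bias in the plan as written is shown.

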### Study Population

Participants will be adult patients (age  $\geq$  18 years) with at least seven patients over the age of 40 years. In addition, at least five patients with a history of heart failure will be included.

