## 4. SUBJECT SELECTION CRITERIA

The following criteria will be used to include subjects in the study:

---

- 4.1 Healthy male and female volunteers who are able to fit in the WCD garment (26 to 56 inches measured circumferentially at the level of the xiphoid process).
- 4.2 Included in this group are at least five healthy subjects with a self-reported history of heart failure.
- 4.3 The subject must be 18 years of age or older on the day of screening, with at least 7 subjects 40 years of age or older on the day of screening.

The following criteria will be used to exclude subjects from the study:

- 4.4 Mental, visual, physical, literacy, and auditory limitations that prevent interaction with the WCD equipment.
- 4.5 Any acute medical conditions that prevent the following maneuvers: lying on back, lying on the right and left side, standing, sitting, and/ or leaning forward when sitting.
- 4.6 Any self-reported shortness of breath, fatigue, swelling of feet, ankles, or legs, and/or chest pain.
- 4.7 Currently has a pacemaker, an implanted cardioverter defibrillator (ICD), or a cardiac resynchronization therapy (CRT) device.
- 4.8 A previous history or current diagnosis of atrial fibrillation.
- 4.9 Employees or family members of Inovise and ZOLL.
- 4.10 Unable or unwilling to provide written informed consent.

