## 9. STUDY SIZE

The study will enroll a minimum of 27 and a maximum of 35 subjects (see section 9.1 for details). At least 5 subjects will have a self-reported history of heart failure.

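### Does scaling the 12-ms margin to a 120-ms cut-off oblige the plan to examine the device difference by EMAT level or heart-failure history?

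*Combined protocol and SAP*

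**What the plan says.** Section 8 takes its margin from a clinical cut-off: 12 ms, "which is 10% of the 120-ms EMAT threshold previously used to identify patients with left ventricular dysfunction". The decision rule is a paired TOST. Equivalence is declared if the 90% confidence interval for the average WCD-minus-AUDICOR difference during quiet sitting lies between -12 and 12 ms.

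Objective 3.1 is to "Compare the heart sound measurements recorded by the AUDICOR® AM device versus those recorded by the WCD while subjects are sitting quietly".

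Criterion 4.1 admits "Healthy male and female volunteers who are able to fit in the WCD garment", and criterion 4.6 excludes "Any self-reported shortness of breath, fatigue, swelling of feet, ankles, or legs, and/or chest pain". Section 9 adds a floor: "At least 5 subjects will have a self-reported history of heart failure". Enrolment is 27 to 35.

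Beyond the TOST, Section 7 plans descriptive and qualitative work to "compare the heart sounds measures for each subject and as a group between the AUDICOR device and WCD device", with no endpoints attached. Section 6 has medical history collected on the case report forms. Neither Section 7 nor Section 8 names a plot or regression of the difference against EMAT level, limits of agreement, or a split by heart-failure history. No expected EMAT distribution is given.

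**The concern.** The margin is justified by a value that separates patients with left ventricular dysfunction, yet the sample is largely symptom-free volunteers. With the minimum of five heart-failure histories, 22 of 27 subjects (81%) or 30 of 35 (86%) may have none. If the WCD's bias grew with EMAT, or differed in heart failure, one pooled mean could average it away. Because the margin is expressed relative to 120 ms, a reader might take a pass as evidence of agreement there. That reading needs the further assumption that bias near 120 ms is also within the margin, and the plan neither states nor checks this.

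The pilot adds some weight. Its mean difference of 7.26 ms in absolute value already uses 61% of the margin (7.26/12), which leaves little room if bias is larger in some subjects.

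**Working it through.** **Inputs.** Margin 12 ms and 90% CI rule (Section 8); pilot n=7, absolute mean 7.26 ms, SD of differences 8.36 ms, 90% CI -13.4 to -1.13 (Section 9.1); N from 27 to 35 with at least five heart-failure histories (Section 9). The group-specific biases below are assumptions; the documents give none.

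**The plan's own figures.**
- Pilot interval: -7.26 ± t(0.95, 6)×8.36/√7 = -7.26 ± 6.14, or -13.40 to -1.12. This matches the printed limits within rounding, so the signed pilot mean is negative.
- Sample size: [8.36×(1.645+1.282)/(12-7.26)]² = 26.6, so 27. This uses z at 1-α, which agrees with the 90% CI rule. Equation 1 as printed, with α/2, gives 32.7, so 33. That mismatch is a separate matter and does not affect this point.

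**What the pooled rule tolerates.** At n=27 the half-width is t(0.95, 26)×8.36/√27 = 2.74 ms. With a sample SD of 8.36, an observed mean passes up to 12-2.74 = 9.26 ms in either direction.

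**Would the rule react to extra bias in heart failure?** Simulated TOST, 22 others plus 5 with heart failure, within-group SD 8.36:

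| Others (ms) | Heart failure (ms) | Pooled mean (ms) | Passes |
|---|---|---|---|
| -7.26 | -7.26 | -7.26 | 89% |
| -6.0 | -12.8 | (22×-6.0+5×-12.8)/27 = -7.26 | 87% |
| -5 | -15 | (22×-5+5×-15)/27 = -6.85 | 90% |
| -7.26 | -12 | (22×-7.26+5×-12)/27 = -8.14 | 74% |
| -7.26 | -12.8 | (22×-7.26+5×-12.8)/27 = -8.29 | 71% |
| -7.26 | -15 | (22×-7.26+5×-15)/27 = -8.69 | 60% |

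Rows two and three make the rule look blind, but there the other 22 subjects are given less bias than the pilot, which offsets the heart-failure excess. In the last three rows the others keep the pilot bias, and the pass rate drops by 15 to 29 points. Section 9.1 does not say whether any pilot subject had heart failure, so the documents favour neither set.

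The offset grows at n=35 (30 plus 5). There -6.0/-12.8 pools to -244/35 = -6.97 and -5/-15 to -225/35 = -6.43. Their pass rates of 96% and 98%, against 95% under constant bias, partly reflect a smaller average bias.

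**What could extra outputs show?**
- Interval for five heart-failure subjects: half-width t(0.95, 4)×8.36/√5 = 7.97 ms. Under constant bias of -7.26 and an SD of 8.36, the lower limit sits near -7.26-7.97 = -15.23. In simulation it falls below -12 about 72% of the time, with no heart-failure effect present.
- In the other direction, that interval lies wholly below -12 only 7% of the time when the heart-failure bias is -12.8, and 17% when it is -15.
- Contrast of 5 against 22: half-width t(0.95, 25)×8.36×√(1/5+1/22) = 7.07 ms.
- Slope of difference on pair mean: with constant bias but unequal device noise (assumed SDs 8 and 2.4 ms, true EMAT SD 12 ms), the mean slope is 0.18 and its 90% CI excludes zero 41% of the time.

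**The case for a change.** The strongest case for a change is that the outputs cost almost nothing. Per-subject EMAT and medical history are already collected, the TOST would stay the sole decision rule, and naming the displays in advance guards against choosing them after seeing the data. A count of subjects at or near 120 ms needs no subgroup power and would show directly whether the sample reached the value that scales the margin. The masking examples also do not hinge on how the pilot SD is read: with the total SD held at 8.36, -5/-15 and -6.0/-12.8 still pass 95% and 90% of the time at n=27.

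Much of this stands. The plan is silent on these displays, a pooled mean can conceal a difference between groups, and a difference-versus-mean plot with the observed EMAT range would be a helpful way to present the planned comparison. What does not stand is the step from there to a defect. The harm requires a reader to infer agreement at 120 ms, which the plan does not assert; Section 8 uses 120 ms only to scale the margin. Heart-failure history is not the same thing as EMAT level, and the documents link neither to values near 120 ms in these volunteers. The planned per-subject comparison, read with the medical history, already supplies the raw material.

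**Conclusion.** No change to the plan is needed. The quantity tested, the average paired difference in quiet sitting, is stated clearly and matches objective 3.1. A pass supports average agreement over the subjects and EMAT values enrolled, and should be read that way.

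The size of any masking is not fixed by the documents: 87 to 90% passing if the other subjects have less bias than the pilot, 60 to 74% if they have the pilot bias, against 89% with constant bias. All of these assume five heart-failure subjects, n=27 and within-group SD 8.36 ms. The 81% and 86% shares without heart-failure history are upper bounds, because five is a minimum.

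Formal subgroup or slope inference would gain little and could mislead, given the 72% and 41% false-alarm figures under the stated assumptions. What remains is a gap in the layout of a descriptive comparison that Section 7 already commits to. Analysts can sensibly fill it with a difference-versus-mean plot and a listing of differences by heart-failure history, without inference. Neither would alter the equivalence decision.
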